## 5.0 Study Treatment

## 5.1 Description of Study Treatment

lvosidenib will be administered orally at a dose of 250 mg or 500 mg (provided as 250 mg strength tablets) daily.

Nivolumab will be administered at 480 mg IV every 28 days.

## 5.2 Study Treatment Packaging and Labeling

lvosidenib will be supplied in appropriate containers with child resistant closures and labeled appropriately as the investigational product for this study.

Packaging and labeling will be prepared to meet all regulatory requirements.

#### 5.3 Study Treatment Storage

lvosidenib and nivolumab must be stored according to the package label.

Ivosidenib should be stored in a secure area according to local regulations. It is the responsibility of the local PI to ensure that ivosidenib is only dispensed to study participants. Ivosidenib must be dispensed only from official study site by authorized personnel according to local regulations.

The product storage manager should ensure that the study treatment is stored in accordance with the environmental conditions (temperature, light, and humidity). If concerns regarding the quality or appearance of the study treatment arise, the study treatment should not be dispensed.

Investigational product (IP) documentation must be maintained and includes all processes required to ensure drug is accurately administered. This includes documentation of drug storage, administration, and as applicable, storage temperatures, reconstitution, and use of required processes (e.g., required diluents, administration sets). A temperature excursion form will be provided at study activation. All temperature excursion must be reported to BMS.

Storage facilities for controlled substances must be securely locked and substantially constructed, with restricted access to prevent theft or diversion, as applicable by local regulations.

Details regarding preparation and administration are provided in the site training materials for AG-120.
For nivolumab, investigational supply is being provided for this study. Please only refer to the nivolumab IB for drug storage, preparation, and administration guidelines to include in the protocol.

### 5.4 Study Treatment Preparation and Administration of Ivosidenib

Daily treatment with ivosidenib will begin on C1D1. Dosing is continuous; there are no planned intercycle rest periods. Participants should be instructed to take their QD dose at approximately the same time each day.

Participants should be instructed to swallow tablets whole and to not chew the tablets. Participants may take ivosidenib tablets with or without food. Participants should be advised that if ivosidenib tablets are taken with food, the participant should avoid grapefruit or grapefruit products and avoid consuming a high-fat meal.

If the participant forgets to take the daily dose, then they should take ivosidenib within 12 h after the missed dose. If more than 12 h have elapsed, then that dose should be omitted, and the participant should resume treatment with the next scheduled dose.

Participants will continue to receive best supportive care throughout the study, regardless of treatment arm. Participants may continue with their assigned study treatment until any of the conditions for withdrawal of study treatments are met - as detailed in Section 4.4.1. For participants who are determined to be on ivosidenib upon radiographic disease progression and demonstrate clinical benefit, Pis, with consult from the Sponsor, may keep the participants on ivosidenib after the disease progression.

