# 4.4.1 Withdrawal from Study Treatment

Participants may discontinue or be discontinued from study treatment at any time. In this situation, a participant without documented progressive disease by the treating investigator should be followed for tumor assessments until the development of progressive disease and/or survival. Participants will be discontinued from study treatment for the following reasons:

- Grade 4 QTcF prolongation.
- Disease progression (participants who are, in the opinion of the treating investigator, benefiting from treatment [e.g., slow progression or immune-related response evaluation] may be allowed to continue on study treatment)
- Severe or unacceptable toxicity
- Death
- Lead Investigator decision
- Subject decision to withdraw from treatment
- Protocol violation: non-adherence to study treatments as required for evaluability (detailed in section 8.1.1) or other protocol requirements.
- Confirmed pregnancy (study therapy should be immediately interrupted based upon a positive urinary human chorionic gonadotropin [hCG] test, and permanently discontinued if confirmed by a serum -hCG test)
- Lost to follow-up

All AEs should be followed until resolution or for a period of 28 days from the last dose of study treatment, whichever is shorter. If the participant withdrew from treatment because of an AE, every

effort must be made to perform protocol-specified safety follow-up procedures. All SAEs that occur up to 100 days post last dose of nivolumab must be reported to BMS World Wide Safety.

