### 8.0 Statistical Analysis Plan and Sample Size Justification

The primary and secondary objectives and endpoints are in Section 2. The accrual goal for this trial is 35 participants evaluable for both safety and efficacy.

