### 8.1 Evaluability

### 8.1.1 Evaluability for Safety

Participants will be evaluable for safety if they receive a minimum of 75% of the first cycle of ivosidenib and have received one dose of nivolumab, unless they experience a DLT. The DLTwindow will be defined as from first dose through completion of the first 28-day cycle.

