### 8.1.2 Evaluability for Efficacy

Patients will be evaluable for the co-primary efficacy objectives of response and PFS at the time of first radiographic assessment at week 12 of the study. Patients must receive a minimum of 75% of the first cycle of ivosidenib and have received one dose of nivolumab to be considered evaluable. Any patient having taken 75% of ivosidenib with clear clinical progression prior to first restaging at will also be evaluable for this objective.

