### with Immunotherapy

### Please carefully read and follow these instructions:

- Bring this Pill Diary and any remaining AG-120 pills to clinic visits so your doctor can make sure that you are taking the pills correctly.
- Store the pills at room temperature at 20°C to 25°C (68°F to 77°F).
- Each dose is \_\_\_\_ pills. Take each dose by mouth at the same time every day with one glass of water. Tablets should be swallowed whole. You can toke the pills with or without meals.
  - If you miss taking a pill on time (a dose is missed) or you vomit after taking the pill, please do not repeat the dose.
  - A dose is missed when more than 2 hours from the normal scheduled dosing time has elapsed.
- In the boxes below, note the date and time each day you take the AG-120 study drug pills:

Patient Initials (FML):	Start Date			
		1	1	
1	1			
Cycle Number		_Dose		
Research Assistant Signature	:			-
Date:	_			

Day 1	Day2	Day3	Day4	Day 5	Day6	Day7
Date:	_ Date:	Date:	Date:	Date:	Date:	Date:
Time:	Time:	Time:	Time:	Time:	Time:	Time:
Days	Day9	Day 10	Dayll	Day 12	Day 13	Day 14
Date:	_ Date:	Date:	Date:	Date:	Date:	Date:
Time:	Time:	Time:	Time:	Time:	Time:	Time:
Day 15	Day 16	Day 17	Day 18	Day 19	Day 20	Day 21
Date:	Date:	Date:	Date:	Date:	Date:	Date:
Time:	Time:	Time:	Time:	Time:	Time:	Time:
Day22	Day23	Day 24	Day25	Day 26	Day 27	Day 28
Date:	_ Date:	Date:	Date:	Date:	Date:	Date:
Time:	Time:	Time:	Time:	Time:	Time:	Time:

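### The pill diary's 2-hour rule for a missed ivosidenib dose contradicts the 12-hour rule in section 5.4, and eight doses skipped under it in Cycle 1 would cost a participant evaluability

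*Combined protocol and SAP*

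**What the plan says.** **Late doses.** Section 5.4 says that after forgetting a dose "they should take ivosidenib within 12 h after the missed dose"; only beyond 12 hours is the dose left out. The pill diary (11.10) sets another limit: "A dose is missed when more than 2 hours from the normal scheduled dosing time has elapsed". Its instruction for that case begins "If you miss taking a pill on time (a dose is missed) or you vomit after taking the pill, please do" and ends by telling the participant not to repeat the dose.

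**Where the dose count matters.** Section 8.1.1 states: "Participants will be evaluable for safety if they receive a minimum of 75% of the first cycle of ivosidenib", with one dose of nivolumab, and exempts anyone who has a DLT. Section 8.1.2 states: "Patients must receive a minimum of 75% of the first cycle of ivosidenib and have received one dose of nivolumab to be considered evaluable". It has no DLT exemption, and its clause on early progression carries the same threshold: "Any patient having taken 75% of ivosidenib with clear clinical progression prior to first restaging". Section 4.4.1 lists this among the reasons for stopping treatment: "Protocol violation: non-adherence to study treatments as required for evaluability". Section 8.0 adds: "The accrual goal for this trial is 35 participants evaluable for both safety and efficacy". Under 5.11, compliance is judged from returned tablets and the diary.

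**Drug order.** Section 5.7 gives nivolumab, then a 30-minute rest, then ivosidenib. Section 5.11 has ivosidenib taken before the nivolumab infusion on clinic days.

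**The concern.** For a dose between 2 and 12 hours late, the protocol body and the diary give different instructions. The diary is the document that the participant fills in at home, and it is also one of the two sources for compliance.

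The 75% rule counts doses taken and ignores their timing, so a late dose taken under 5.4 costs nothing. The diary can turn that late dose into an untaken one. A participant who follows the diary faithfully could then drop out of the efficacy-evaluable set, usually out of the safety-evaluable set too, and meet a listed reason for stopping treatment. An early clinical progressor below 75% would not qualify under the early-progression clause in 8.1.2. Since the accrual goal is stated in evaluable participants, such a person might be replaced rather than counted as a failure, although the documents do not spell out replacement.

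**Working it through.** **Plan's own figure.** The Simon design continues with at least 3 positive outcomes in 18 and rejects with at least 7 in 35 (8.2.1). The probability of rejecting is the sum over x = 3 to 18 of P(X1 = x) × P(X2 ≥ 7 − x), with X1 ~ Bin(18, p) and X2 ~ Bin(17, p). This gives 0.0474 at p = 0.1 and 0.9016 at p = 0.3, which agrees with the stated alpha of 0.05 and 90% power. These calculations take 35 evaluable participants as given, so the diary wording does not change them.

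**Evaluability threshold.** Inputs: once-daily dosing on a 28-day cycle (3.1) and a 75% minimum (8.1.1, 8.1.2).
- 0.75 × 28 = 21 doses needed.
- 7 skipped: 21/28 = 75.0%, evaluable.
- 8 skipped: 20/28 = 71.4%, not evaluable.
- Same eight doses taken late under 5.4: 28/28 = 100%, evaluable.

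Section 3.1 allows cycles of 28 ± 2 days. The smallest failing count is 7 for 26 or 27 days and 8 for 28 to 30 days. The skips need not be consecutive, and doses omitted for other reasons count towards the same limit.

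**How many participants.** The documents give no rate, so everything here is assumption. Let q be the chance that a dose is 2–12 hours late, and suppose that every such dose is skipped. The quantity is P(X ≥ 8). Two settings are compared:
- No correction during Cycle 1: the 27 doses after C1D1 are at risk.
- The C1D15 visit restores the 12-hour rule: only the 13 doses on Days 2–14 are at risk.

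Each is computed with independent lateness (binomial) and with lateness clustered within participants (beta-binomial, assumed ICC 0.1, so a = 9q and b = 9(1 − q)).

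| q | 27 doses, independent | 27 doses, ICC 0.1 | 13 doses, independent | 13 doses, ICC 0.1 |
|---|---|---|---|---|
| 5% | 0.004% | 2.6% | <0.001% | 0.13% |
| 10% | 0.4% | 7.9% | 0.001% | 0.5% |
| 15% | 4.0% | 16.0% | 0.016% | 1.3% |
| 20% | 15.6% | 26.6% | 0.12% | 2.8% |

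The extreme cell without correction is 0.266 × 35 = 9.3 participants per 35 started. With a Day 15 correction it is 0.028 × 35 = 1.0. At q = 10% over 27 doses, changing the ICC from 0.05 to 0.2 moves the result from 4.5% to 11.5%. With the diary aligned to 5.4, the figure from this cause is 0 in every cell.

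**The case against.** Several points on the other side stand.

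- **The diary's verb.** It says not to repeat a dose, in a line shared with vomited doses, and never says to skip a late one. It could be meant only to bar double dosing. Because the diary supplies its own 2-hour definition of a missed dose and gives no permission to take it late, skipping remains the natural reading, but it is a reading.
- **Other instructions.** Section 5.12 promises participants home-administration instructions, and 5.3 refers to site training materials. Neither is in the file, and either could state the 12-hour rule.
- **The Day 15 check.** Visits fall on Days 1 and 15 of Cycle 1 (3.1), and the diary asks participants to bring diary and tablets so that use can be checked. A correction there removes most of the possible effect.
- **The DLT exemption.** A participant with a DLT stays evaluable for safety however many doses were skipped. The loss is unconditional only for efficacy.

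A reader might infer from the right-hand figures for 27 doses that up to a quarter of participants could be lost. The documents do not support that. Those figures need frequent lateness, strong clustering, every late dose skipped and nothing corrected at Day 15.

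A reader might also infer that the opposite drug orders undermine the attribution of infusion reactions or the DLT count. They do not. Section 5.7 already provides one conservative management scheme for reactions of unclear cause. Its instruction to give no more study drug at that visit follows directly on stopping the infusion. Section 7.5 counts qualifying events unless clearly due to an extraneous cause, whichever study drug produced them. With a mean half-life of 38.4 to 86.2 hours (1.4.3.1) and daily dosing, ivosidenib is present at later infusions in either order, so the order matters mainly at C1D1.

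**Conclusion.** The conflict between 5.4 and the diary is real and is in current text. Its consequence for one participant is exact: eight skipped doses in a 28-day Cycle 1 give 71.4%, with loss of efficacy evaluability and, absent a DLT, of safety evaluability, where 5.4 would have given 100%. This rests on reading the diary's instruction as skip.

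The number of participants affected cannot be known from the documents. It is probably very small: under 0.5% if lateness is 10% or less and evenly spread, and at most 2.8% in the scenarios shown if the Day 15 review corrects the practice. The operating characteristics of the design do not change. Selective loss of early progressors from the primary denominator is possible in principle, but nothing in the documents shows that it would be material. This is a minor point, worth making because the correction is so cheap. The drug-order conflict is a consistency matter only.

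**What to change.** In the diary (11.10), replace the 2-hour sentence with: *If you forget a dose, take it if it is within 12 hours of your usual time; if more than 12 hours have passed, skip it and take the next dose as scheduled.* Reduce the other line to: *If you vomit after taking the pill, do not repeat the dose.* Check that the home-administration instructions and site training materials agree.

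For drug order, the sponsor should choose one sequence and state it identically in 5.7 and 5.11.

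The cost is two diary sentences and one order sentence. Under 9.5 the change needs IRB approval and then affiliate IRB approval within 3 months, so it can go with the next amendment. Design, sample size and analysis stay as they are.

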# 5.5 Criteria for Dose Modification, Discontinuation of Study Treatment, and Continuation Beyond Radiographic Progression

### 5.5.1 Study Treatment Dose Modification and Discontinuation Criteria

### 5.5.1.1 Dose Modifications and Delays

Dose reductions or dose escalations of nivolumab are not permitted. Nivolumab may continue if the ivosidenib is held unless the hold of ivosidenib is for more than 28 days. If a safety issue arises that is related to nivolumab, the nivolumab should be withheld or permanently discontinued (Section 5.9). In such a case, continuing ivosidenib may be allowed after consultation with the PI.

For any AE, including AEs not specifically mentioned in Table 1, the treating investigator may decide to delay dosing or modify the dose of ivosidenib based on clinical judgment. Dose modifications of ivosidenib from 500 mg to 250 mg will be permitted on study for management of AEs (Table 1). If more than one AE occurs that would require a dose modification, upon resolution of all AEs to baseline or Grade 1, ivosidenib should be dose reduced to 250 mg. Dose reductions below 250 mg are not permitted. If the AE is thought to be related to the ivosidenib, the nivolumab will continue to be dosed as per protocol schedule.

Dose delays for reasons other than management of AEs are discouraged. Dose delays up to 28 days will be permitted at the discretion of the lead investigator.

If the participant cannot resume ivosidenib within 28 days, the participant should be discontinued from both study medications. If ivosidenib is discontinued, the participant will complete the EOT and Followup Visits, and then enter PFS follow-up (if disease has not progressed). Exemptions may be considered for those participants who are determined by the investigator to have received clinical benefit from treatment. If a dose is delayed for the management of an AE, the participant should resume the study at the next planned visit within a dosing cycle. This determination will be at the discretion of the treating physician.

AEs	Action
Grade 2 nausea or vomiting (related or unrelated)	
 
Consider holding dose of ivosidenib until resolution of AE to Grade 
 
within 28 days of supportive therapy.
 
 
 
Manage with supportive therapy according to the institutional standard of care.
 
May resume ivosidenib at same dose.
 

Grade 3 AEs (related, first event)	
 
Hold dose of ivosidenib until resolution to Grade 1 or baseline within 28 days of supportive therapy and then resume dose.
 
Manage with supportive therapy according to the institutional standard of care.
 

	
 
If the Grade 3 AE recurs (a second time), consider reducing ivosidenib to 250 mg. Re-escalation may be permitted after discussion with the Lead Investigator.
 

	
 
If the Grade 3 AE recurs (a third time) despite dose reduction of ivosidenib, then consider discontinuing ivosidenib in consultation with the Lead Investigator.
 

Grade 4 AEs (related, first event)	
 
Hold ivosidenib
 
Manage with supportive therapy according to the institutional standard of care.
 
If the AE resolves to Grade 1 or baseline within 28 days, then restart ivosidenib dosing at 250 mg in consultation with the Lead Investigator.
 
If the AE does not resolve to Grade 1 or baseline within 28 days, consider discontinuing study treatment in consultation with the Lead Investigator.
 
If the Grade 4 AE recurs (a second time), despite dose reduction, ivosidenib should be discontinued in consultation with the Lead Investigator.
 

\*See Table 2 for specific dose modifications for QTcF prolongation.

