# Table 2: Management of QT Prolongation by CTCAE Grade

# 5.7 Treatment of Study Drug-related Infusion Reactions

Nivolumab and the combination therapies may induce infusion or hypersensitivity reactions. If such a reaction were to occur, it may manifest with fever, chills, rigors, headache, rash, pruritus, arthralgia, hypo- or hypertension, bronchospasm, or other symptoms.

Infusion reactions should be graded according to CTCAE vs guidelines. Any Grade 3 or Grade 4 infusion reaction should be reported within 24 h to the PI or designee and reported as an SAE if it meets the criteria.

The nivolumab 30-min infusion will be administered first, with a 30-min rest, followed by the administration of ivosidinib. It may be unclear if an infusion reaction is due to the combination therapy, nivolumab, or to both study drugs. Therefore, one set of treatment recommendations (based on the most conservative treatments for infusion reactions due to either study drug) is

provided below and may be modified based on clinical judgment, local treatment standards and guidelines, and/or specific symptoms, as appropriate:

**For Grade 1 symptoms:** Mild reaction (e.g., localized cutaneous reactions including mild pruritus, flushing, rash), requires infusion rate to be decreased; intervention may be indicated.

Decrease the rate of the study drug infusion until recovery from symptoms.

Remain at bedside and monitor the participant's vital signs until resolution of symptoms. Diphenhydramine 50 mg may be administered at the discretion of the treating physician.

When symptoms resolve, restart the infusion at the original infusion rate.

If a participant has an infusion reaction with nivolumab, combination therapy can be given (without prophylactic medications) if the infusion reaction resolves within 3 h. For scheduling purposes, infusion may be given the next day. Prophylactic pre-infusion medications should be given prior to all subsequent nivolumab infusions.

If a participant has an infusion reaction, prophylactic pre-infusion medications should be given prior to all subsequent infusions.

The following prophylactic pre-infusion medications are recommended prior to future infusions: diphenhydramine 50 mg (or equivalent) and/or paracetamol (acetaminophen) 325 to 1,000 mg at least 30 min before additional study drug administrations.

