### 5.8 Nivolumab AEs

Nivolumab treatment should be permanently discontinued for the following:

Any Grade 2 drug-related uveitis, eye pain, or blurred vision that does not respond to topical therapy and does not improve to Grade 1 severity within the OR requires systemic treatment

Any Grade 3 non-skin, drug-related AE lasting> 7 days or recurs, with the following exceptions for laboratory abnormalities, diarrhea, drug-related uveitis, pneumonitis, bronchospasm, hypersensitivity reactions, infusion reactions, and endocrinopathies:

- Grade 3 drug-related diarrhea, uveitis, pneumonitis, bronchospasm, hypersensitivity reaction, or infusion reaction of any duration requires discontinuation.
- Grade 3 drug-related endocrinopathies adequately controlled with only physiologic hormone replacement do not require discontinuation.

- Grade 3 drug-related laboratory abnormalities do not require treatment discontinuation except for the following:
  - Grade 3 drug-related thrombocytopenia > 7 days or associated with bleeding requires discontinuation
  - o Any drug-related liver function test (LFT) abnormality that meets the following criteria require discontinuation:
    - Grade 3 drug-related AST, ALT, or total bilirubin requires discontinuation
    - Concurrent AST or ALT> 3x ULN and total bilirubin > 2x ULN

Any drug-related Grade 4 endocrinopathy and Grade 3 adrenal insufficiency requires discontinuation.

Any Grade 4 drug-related AE or laboratory abnormality (including but not limited to creatinine, AST, ALT, or total bilirubin), except for the following events, which do not require discontinuation:

- Grade 4 neutropenia ::; 7 days
- Grade 4 lymphopenia or leukopenia
- Isolated Grade 4 amylase or lipase abnormalities that are not associated with symptoms or clinical manifestations of pancreatitis
- Isolated Grade 4 electrolyte imbalances/abnormalities that are not associated with clinical sequelae and are corrected with supplementation/appropriate management within 72 h of their onset

Any drug-related Grade 4 endocrinopathy and Grade 3 adrenal insufficiency requires discontinuation.

Any event that leads to delay in dosing lasting> 8 weeks from the previous dose requires discontinuation, with the following exceptions:

- Dosing delays to allow for prolonged steroid tapers to manage drug-related AEs are allowed.
- Dosing delays lasting > 8 weeks from the previous dose that occur for non-drug-related reasons may be allowed if approved by the Lead Investigator.

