# 5.9 Management of Nivolumab AEs

Participants should receive appropriate supportive care measures as deemed necessary by the treating investigator. Where appropriate, these guidelines include the use of oral or IV treatment with corticosteroids as well as additional anti-inflammatory agents if symptoms do not improve with administration of corticosteroids. Note that several courses of steroid tapering may be necessary as symptoms may worsen when the steroid dose is decreased. For each disorder, attempts should be made to rule out other causes such as metastatic disease or bacterial or viral infection, which might require additional supportive care. The treatment guidelines are intended to be applied when the investigator determines the events to be related to nivolumab.

It may be necessary to perform conditional procedures such as bronchoscopy, endoscopy, or skin photography as part of evaluation of the event.

- Pneumonitis:
  - For Grade 2 events, treat with systemic corticosteroids. When symptoms improve to Grade 1 or less, steroid taper should be started and continued over no less than 4 weeks.
  - o For **Grade 3-4 events**, immediately treat with IV steroids. Administer additional antiinflammatory measures, as needed.
  - o Add prophylactic antibiotics for opportunistic infections in the case of prolonged steroid administration.
- Diarrhea/Colitis:

Participants should be carefully monitored for signs and symptoms of enterocolitis (such as diarrhea, abdominal pain, blood or mucus in stool, with or without fever) and of bowel perforation (such as peritoneal signs and ileus).

- All participants who experience diarrhea/colitis should be advised to drink liberal quantities of clear fluids. If sufficient oral fluid intake is not feasible, fluid and electrolytes should be substituted via IV infusion. For Grade 2 or higher diarrhea, consider GI consultation and endoscopy to confirm or rule out colitis.
- o For **Grade 2 diarrhea/colitis** that persists greater than 3 days, administer oral corticosteroids.
- For **Grade 3 or 4 diarrhea/colitis** that persists> 1 week, treat with IV steroids followed by high dose oral steroids.
- o When symptoms improve to Grade 1 or less, steroid taper should be started and continued over no less than 4 weeks.
- o Type 1 diabetes mellitus (if new onset, including diabetic ketoacidosis [DKA]) or Grade 3 Hyperglycemia, if associated with ketosis (ketonuria) or metabolic acidosis (DKA)

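### Section 5.5.1.1 continues nivolumab after an ivosidenib-related AE without limiting this to ivosidenib alone, so an AE attributed to both drugs gets conflicting instructions, in some cases against a mandatory stop in Section 5.8

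*Combined protocol and SAP*

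**What the plan says.** Section 5.5.1.1 gives three instructions on nivolumab.

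- When ivosidenib is held, nivolumab may go on unless the hold exceeds 28 days.
- For nivolumab toxicity: "If a safety issue arises that is related to nivolumab, the nivolumab should be withheld or permanently discontinued (Section 5.9". The only section cited is 5.9.
- For ivosidenib toxicity: "If the AE is thought to be related to the ivosidenib, the nivolumab will continue to be dosed as per protocol schedule".

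Table 1 in the same section covers ivosidenib dosing. For a first related Grade 3 AE it reads "Hold dose of ivosidenib until resolution to Grade 1 or baseline within 28 days of supportive therapy and then resume dose".

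Section 5.8 opens its list with "Nivolumab treatment should be permanently discontinued for the following". One entry is "Grade 3 drug-related diarrhea, uveitis, pneumonitis, bronchospasm, hypersensitivity reaction, or infusion reaction of any duration requires discontinuation". Others include Grade 3 drug-related AST, ALT or total bilirubin, and any Grade 4 drug-related event outside four listed exceptions.

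Section 5.9 covers treatment of nivolumab AEs and sets its scope as follows: "The treatment guidelines are intended to be applied when the investigator determines the events to be related to nivolumab". Section 5.7 recognises that either or both drugs may be responsible and gives one set of recommendations, "based on the most conservative treatments for infusion reactions due to either study drug". It covers infusion and hypersensitivity reactions only.

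**The concern.** In a two-drug combination some AEs will be attributed to both agents. Section 7.1.5 allows for this, since its definition of a related AE refers to the drug or drugs. Such an AE is related to ivosidenib, which triggers the instruction to continue nivolumab. It is also related to nivolumab, which triggers the instruction to withhold or stop it. Nothing in Section 5.5.1.1 says which sentence yields.

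What is at stake is participant safety. A site that follows the continue sentence literally could give the next nivolumab infusion after an event for which Section 5.8 requires permanent discontinuation.

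**Working it through.** No figure in the plan is in question, so the check is textual: take each possible attribution and read off what each section says about nivolumab.

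| Attribution of the AE | Section 5.5.1.1 | Section 5.8, if the event is listed | Consistent? |
|---|---|---|---|
| Nivolumab only | Withhold or discontinue | Discontinue permanently | Yes |
| Ivosidenib only | Continue on schedule | Unclear: the list says *drug-related* without naming the drug | Depends on the reading |
| Both drugs | Withhold or discontinue, and also continue on schedule | Discontinue permanently | No |

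**Worked case: first Grade 3 diarrhea attributed to both drugs.**

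1. Table 1 holds ivosidenib until recovery, allowing up to 28 days.
2. The ivosidenib sentence in Section 5.5.1.1 keeps nivolumab on its 28-day schedule.
3. The nivolumab sentence in Section 5.5.1.1 withholds or stops nivolumab and points to Section 5.9.
4. For this event, once it has lasted more than a week, Section 5.9 says to "treat with IV steroids followed by high dose oral steroids". It gives no criterion for withholding or stopping nivolumab.
5. Section 5.8, which Section 5.5.1.1 does not cite, stops nivolumab permanently whatever the duration of the event.

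Steps 2 and 5 cannot both be followed. The same contradiction arises for a jointly attributed Grade 3 AST, ALT or bilirubin elevation, and for a jointly attributed Grade 4 event outside the four exceptions. None of those exceptions turns on attribution to ivosidenib.

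**Is there a rule that settles it?** Section 5.7 does so for infusion and hypersensitivity reactions by taking the most conservative course. No equivalent statement covers other AEs. The causality table in Section 7.1.5 grades relatedness to study drug and does not require a separate judgment for each agent.

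**Does it reach the analysis?** Evaluability in Sections 8.1.1 and 8.1.2 requires one nivolumab dose, so stopping or continuing after that dose does not change who is counted. The Simon boundaries in Section 8.2.1 (3 or more of 18, then 7 or more of 35) and the DLT stopping table do not depend on this sentence.

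**The case against.** The strongest reply is that the sentence is clear in its place. Section 5.5.1.1 deals with nivolumab in one paragraph and with ivosidenib delays and reductions in the next, and the sentence closes the second. Read there, it says only that an ivosidenib toxicity need not interrupt nivolumab. A joint AE is still related to nivolumab, so the first paragraph applies, and so does Section 5.8 as the more specific rule. Section 3.1 also discontinues either agent for severe toxicity, Section 4.4.1 lists severe toxicity as a reason to stop study treatment, and Section 5.8 ends with a provision for any event that poses substantial risk if nivolumab goes on. The wrong cross-reference is one of several: Section 6.4.2, for instance, sends QT management to Section 5.7 when it is in Section 5.6.

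Most of this stands. It shows the probable intent and makes harm unlikely, since a site would have to pass over several provisions to keep dosing. But the general rules neither qualify the continue sentence nor rank it below Section 5.8. The cross-reference is a numbering slip, yet here it leads away from the stopping criteria.

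A reader might also infer that many participants are exposed. The documents do not support that. Section 1.5 reports diarrhea in 26.2% of 168 participants on ivosidenib, but that figure covers any grade and any cause. The same section does not name diarrhea, AST, ALT or bilirubin among Grade 3 AEs seen in more than 2 participants. If that list is complete, each occurred at Grade 3 in at most 2/168 = 1.2% on ivosidenib alone. The rate on the combination is not given. Counting the event types in Section 5.8 does not measure risk either.

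**Conclusion.** The point holds as a minor correction to a safety instruction. For an AE attributed to both drugs, Section 5.5.1.1 contains two opposing nivolumab instructions, and for events on the Section 5.8 list one of them contradicts a mandatory permanent stop. No text outside Section 5.7 says which prevails.

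This rests on two readings: that joint attribution is possible, which Section 7.1.5 supports, and that *drug-related* in Section 5.8 includes events attributed to both drugs, which its wording does not exclude. No event rate is claimed.

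It would go too far to conclude that the plan intends nivolumab to continue after a Section 5.8 event, or that the efficacy conclusions are affected. The first runs against the specific stopping list and the general severe-toxicity rules. On the second, the primary analysis, type I error and power do not depend on this sentence.

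**What to change.** Make two edits, both in Section 5.5.1.1.

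1. Replace the continue sentence with one to this effect: if an AE is attributed to ivosidenib alone and not to nivolumab, nivolumab stays on its schedule unless a Section 5.8 discontinuation criterion is met; if attribution is joint or uncertain, the nivolumab rules in Sections 5.8 and 5.9 apply in addition to Table 1.
2. In the nivolumab sentence, change the cross-reference from Section 5.9 alone to Sections 5.8 and 5.9.

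Leave *drug-related* in Section 5.8 as it stands. Changing it to nivolumab-related would allow events attributed to ivosidenib alone to drop off the stopping list. Attribution in a combination is uncertain, so a misattributed event could then lose its stop.

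The cost is amendment wording in one section. Some jointly attributed events will stop nivolumab that a site might otherwise have continued.
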